The present study presents various complications that are possible with the vertical ridge augmentation procedures, both with a d-PTFE and titanium mesh. The common complications that can occur are: exposure of d-PTFE membrane or titanium mesh, infection, paresthesia, postoperative pain, swelling and bleeding. However, there is no additional risk participating in the study compared to the standard of care of vertical ridge augmentation. d-PTFE membrane cannot be used under load bearing conditions, which is not related to the study procedure.

As with surgeries involving metallic implants there is a chance for foreign body sensitivity. Where material sensitivity is suspected appropriate tests should be made to rule out this possibility prior to implantation.

Risk of bone core biopsy

In the bone core biopsy, a trephine will be used and a bone core sample of the hard tissue will be collected and finalized with standard bur prior to implant placement. No more than the standard amount of bone will be removed for this study. There is no additional risk related to this procedure. The risk associated with bone biopsy is over-drilling of bone (create a bigger hole than the size of hole that is necessary for bone core) when harvesting a bone piece. However, the risks associated with bone biopsy are minimal because a bone core drill is smaller than a standard implant drill, which is necessary to place an implant.

2) Benefits

There is no medical benefit to the subject for participating in this study.

3) Alternatives

Study subjects will be informed that they have the right to withdraw from the study at any time for any reason, without prejudice to their dental care. The alternative is not to participate in the study. Patients may receive the standard care for vertical augmentation procedures from postgraduate students of the TUSDM periodontology clinic at standard clinic fees.

E) Study Procedures

Visit 1: Screening

Informed consent will be obtained by the principal investigator or a co-investigator. The subjects will be instructed to read the informed consent form (ICF), given ample time to have any questions answered, and then instructed to sign the ICF. Subject will be given a copy of the ICF.

Subject will be asked to complete demographic information and a medical history.

Inclusion/exclusion criteria will be evaluated.

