Bone harvesting using bone scrapers will be performed during GBR procedures with both techniques (d-PTFE and Ti-mesh). Bone harvesting using bone scrapers is for harvesting particulate autogenous bone graft material. We will use a mixture of 50:50 DBBM and autogenous bone graft material for all vertical augmentation procedures in the study. Particulate autogenous bone graft will be harvested from the retromolar region of the mandible. This area is just next to the area of GBR procedures (posterior mandible) and will be visible after flap elevation for vertical augmentation. Therefore, we do not need any additional steps except harvesting autogenous bone graft. Intraoral harvesting by bone scrapers from the retromolar region is a simple and safe method for collecting cortical bone chips.

The intrasurgical clinical measurements of the ridge height will be taken during surgery. The distance between the top of the tenting screw and bone crest will be measured with a periodontal probe during the procedure.

Duration of each procedure and surgical complications including flap tear and bleeding will be collected. All outcome measurements will be performed by a Co-I who did not perform the surgery.

The subject will be asked to complete a pain/discomfort survey using VAS scale from zero to ten. A medication log will be given to the patient to track the number of pills of the prescribed painkiller they have taken in order to examine the amount of pain after the surgical procedures. The mean number of pills used after surgical procedures will be analyzed.

Post-operative medication will be prescribed following TUSDM standard of care guidelines.

Visit 3 (7±3 days after procedure): Post-operative Follow-up

Medical history will be reviewed as standard of care. Eligibility and subject withdrawal criteria will be reviewed to ensure the subject still qualifies for the study.

Each subject will have a post-operative visit, which is standard practice at TUSDM periodontology clinic. Standard of care procedures including suture removal and evaluation of surgical site will be performed.

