Radiographs will be taken. It is standard of care to have radiographs taken prior to implant placement. The post-operative (after the vertical GBR augmentation procedure) height of the bony crest will be evaluated on the radiographs taken as part of standard of care.

Visit 6 (Up to 1 month after Visit 5): Bone core harvesting, implant placement visit

Medical history will be reviewed as standard of care. Eligibility and subject withdrawal criteria will be reviewed to ensure the subject still qualifies for the study.

The subject will present for their regularly scheduled implant placement. The following steps will be performed following standard of care procedures: local anesthesia, muco-periosteal incision, full thickness flap reflection, membrane (Ti-mesh/d-PTFE) removal, clinical measurements, tenting screws removal, bone core harvesting, implant osteotomy, implant placement, and sutures.

The intrasurgical clinical measurements of the ridge height will be taken at during implant placement surgery. The distance between the top of the tenting screw and bone crest will be measured with a periodontal probe during the procedure. The bone height gain will be calculated by subtracting the second measurement from the first measurement (taken during initial surgery).

At the time of the implant placement a bone core will be harvested from each site of the implant locations for histological analysis. For the bone samples in this study, a hollow (trephine) bur, rather than solid bur, will be used to allow for sampling. A trephine bur with 3-4 mm diameter will be used. The core size will not exceed the amount of bone removal required for designated implants. Removal of bone is standard during implant placement in order to create space for the fixture.

The bone core biopsies will be placed in fixative and labeled with subject ID. The collected bone samples will be placed in alcohol for storage and stored in a basic science laboratory DHS-635.

The implant placement will not be considered a part of this study.

After Visit 6 - Laboratory analysis of bone core sample

Histological slides will be prepared and histomorphometric analysis will be performed by the commercial laboratory. The samples will be coded as subject numbers and histological analysis will be blinded. All collected bone core samples will be shipped to the laboratory by PI or Co-I.

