An unanticipated problem is an incident, experience, or outcome that meets all of the following criteria: 1) The nature, severity, or frequency is unexpected for the subject population or research activities as described in the current IRB approved protocol, supporting documents, and the ICF(s); 2) it is related or possibly related to participation in the research; 3) it suggests the research may place the subject or others at a greater risk of harm than was previously recognized.

Unanticipated problems will be recorded in source documents and on case report forms. Unanticipated problems will be reported to the IRB within 5 business days. An initial report will be submitted to the IRB no later than 2 business days after the PI/study team become aware of the problem, as well.

2) Reporting

Notification of the IRB of any protocol deviation, including to protect the life or physical well being of a subject in an emergency, shall be given to the IRB as they occur throughout the course of the study.

Progress reports on the investigation shall be submitted to the IRB at regular intervals, but in no event less often than yearly.

A final study report shall be submitted to the IRB following termination or completion of the study. Study completion will be defined as completing assessments on the last subject.

G) Subject Participation

1) Screening

The principal investigator or her representative will conduct screening examinations to identify subjects who meet the inclusion/exclusion criteria for enrollment into the study.

2) Informed Consent

The principal investigator or her representative will introduce the study.

Consenting will take place in a private clinic bay area and the patient will be given as much time as he/she needs to consider participation. The participant will be invited to include or exclude any associates (e.g., loved ones) in the consent process.

Patients will be asked to read the consent form and given ample opportunity to have their questions answered. To avoid coercion, the consenting investigator will read through the copy of the consent form with the participant section by section, making sure the participant understands each section and has an opportunity to ask questions. If at any time the participant indicates s/he is not interested in participation, the meeting will end.

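### No study safety collection is scheduled after Visit 6, the operation that removes both barriers and takes the research bone core

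*Combined protocol and SAP*

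**What the plan says.** Section III.E sets the last visit as "Visit 6 (Up to 1 month after Visit 5): Bone core harvesting, implant placement visit". After incision and flap reflection, its steps are "membrane (Ti-mesh/d-PTFE) removal, clinical measurements, tenting screws removal, bone core harvesting, implant osteotomy, implant placement, and sutures". Removing the randomised devices, taking the Aim 1 measurement and taking the Aim 3 core thus all fall in one operation. The same section says of the implant: "The implant placement will not be considered a part of this study". The only later entry is "After Visit 6 - Laboratory analysis of bone core sample", which involves no contact with the subject.

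Table 1 ends at V6. It marks Adverse Event Assessment at V2, V4, V5 and V6, Complication Evaluation at V3 to V5, and VAS scoring at V2 to V5.

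After the augmentation surgery the plan is fuller. Visits 3 and 4 fall at 7±3 and 21±3 days, and for both the text says: "Each subject will have a post-operative visit, which is standard practice at TUSDM periodontology clinic". Visit 5 follows 6±1 months after Visit 4.

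Section III.F, Reporting, closes the study thus: "Study completion will be defined as completing assessments on the last subject".

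**The concern.** A same-day check can record what happens during surgery, but not what develops once the subject has gone home. For the augmentation surgery the protocol lists the usual complications as "exposure of d-PTFE membrane or titanium mesh, infection, paresthesia, postoperative pain, swelling and bleeding". It looks for such events days, weeks and months after Visit 2. Visit 6 is also a flap operation with sutures, yet nobody is scheduled to look afterwards.

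If the schedule is followed exactly, the adverse event data for barrier removal and core harvest will hold intraoperative and same-day events only. A low or zero count would then reflect the schedule as much as the procedures. A report reader could take it as evidence that these steps were uneventful. An event that begins at Visit 6 also has no stated route for follow-up.

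**Working it through.** The plan gives no figure for this point, so the check sets the schedule for the two operations side by side.

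**Scheduled collection after each operation (III.E and Table 1)**

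| | After the Visit 2 operation | After the Visit 6 operation |
|---|---|---|
| Visits | V3 at day 4–10 (7±3), V4 at day 18–24 (21±3), V5 at 6±1 months after V4 | none |
| Complication Evaluation | 3 (V3, V4, V5) | 0 |
| VAS survey | 3 (V3, V4, V5) | 0 |
| Adverse Event Assessment on a later day | V4, V5, V6 | 0 |

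The table marks were read from extracted text, but the result does not depend on their exact alignment, because there is no column after V6.

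**Does other text close the gap?**

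- The interim follow-up visits (III.E, end of Visit 4) belong to the six months after the augmentation surgery, so they come before Visit 6.
- The principal investigator's decision on further observation covers withdrawn subjects (III.D, withdrawal criteria) and study termination (III.K). It does not cover subjects who complete.
- The adverse event definition (III.F) has no end date. A late event that a subject reports could be recorded, but nothing provides for finding one.
- The data safety monitoring plan (III.G.8) works from case report forms, source documents and event tracking. None of these has a scheduled input after Visit 6.
- The exclusion of implant placement does not cover barrier removal, the clinical measurement or the core.

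**Number affected.** The plan is for 10 subjects (III.B). Each has a barrier on both sides, so 10 × 2 = 20 sides. That both sides are re-entered at Visit 6 is inferred from the single visit; the text does not state it.

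**What could go unseen.** The documents give no rate of delayed events, so the per-subject risk p is an assumption. The chance of at least one affected subject among 10 is 1 − (1 − p)^10:

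- p = 5%: 1 − 0.95^10 = 0.401
- p = 10%: 1 − 0.90^10 = 0.651
- p = 20%: 1 − 0.80^10 = 0.893

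Across this range it is far from remote that a delayed event occurs which the schedule has no planned means of detecting.

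**What one added check can show.** Even with complete follow-up, 0 affected of 10 leaves a one-sided 95% upper limit of 1 − 0.05^(1/10) = 0.259, or about 26%. Added data would be descriptive, not proof of safety.

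**The case against.** The strongest reply is that the trial's morbidity aim does not need this information. Aim 2 concerns complications of the augmentation procedure, and Table 1 ends Complication Evaluation and VAS at Visit 5 to match. A reader might infer that removal morbidity is a stated part of the second goal and is being lost. The documents do not say so: the rationale speaks only of morbidity, and Aim 2 ties it to augmentation. No declared endpoint is lost.

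Four further limits stand.

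- **Over-drilling.** The protocol says "The risk associated with bone biopsy is over-drilling of bone", and a reader might infer that this risk goes unobserved. It happens during harvest, so the Visit 6 assessment can record it that day.
- **Paresthesia from the first surgery.** A reader might infer that its persistence cannot be judged. Visit 5 is at least 5 months after Visit 4, which is itself at least 18 days after surgery. A case still open at Visit 6 has therefore lasted more than five months and can already be judged.
- **Additional risk of the core.** The biopsy text denies additional risk and then names a minimal one. In context it compares the core with standard implant drilling. That is loose wording, not a contradiction that matters here.
- **Attribution.** Removal, coring, osteotomy and implant placement share one flap and one day. A later infection or nerve symptom cannot be assigned to the core alone.

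It is also fair that the clinic probably sees patients after implant surgery, since it calls a post-operative visit standard practice after augmentation. But the documents describe no such visit after Visit 6 and link none to study data. That makes the remedy easy, but it does not supply the data.

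**Conclusion.** The point holds as a gap in scheduled safety collection: 0 contacts after the Visit 6 operation, against 3 visits with complication evaluation after Visit 2, for all 10 planned subjects and, by inference, up to 20 sides. It would be too strong to say that late events cannot enter the record, because the open-ended definition admits a volunteered report.

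The consequence is limited. The plan cannot support a claim that barrier removal and coring were free of complications. Height gain and histology come from Visit 6 itself, and the Aim 2 endpoint is collected through Visit 5, so none of the three aims is affected. The change should be made because it is cheap, not because the trial's conclusions depend on it.

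The conclusion assumes that Table 1 and the visit text list all study contacts, and that collection ends at Visit 6 because nothing later is scheduled; no end date is stated.

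**What to change.** - Add one Adverse Event Assessment after Visit 6, by axiUm record review or a telephone call. The 7±3 day window of Visit 3 could be reused. Reviewing axiUm is already a study method at Visit 5.
- Record events by side, for example infection, swelling, bleeding or new paresthesia. Report them descriptively as events after the combined removal, core and implant operation, and do not attribute them to the core alone.
- State that events beginning at Visit 6 are followed through the clinic record.
- Define study completion as completion of this last safety contact for the last subject.

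The cost is a column in Table 1, a short case report form page and one review or call per subject, with no new procedure. It needs a formal IRB-approved amendment (III.J) and keeps each subject in the study about one to two weeks longer. A record review finds only what the clinic wrote down, so the report should say which method was used for each subject.

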A power calculation was performed in nQuery Advisor (version 7.0) with the following assumptions: a type I error of 5%; a type II error of 7%; the titanium mesh group has a mean (SD) height gain of 5.2 (0.79) mm (Artzi 2003)¹⁵; the e-PTFE group has a mean (SD) height gain of 3.15 (1.12) mm (Simion 2007)⁶. The minimum sample size necessary was determined to be 7 subjects. To account for potential dropout, the study population will be increased to include 10 subjects. Up to 15 subjects will be consented (and considered enrolled) into the study to achieve these goals.

Statistical Analysis:

Counts and percentages, will be reported for categorical data. Mean and standard deviations will be reported for continuous data.

1. For the Aim 1, the height gain will be measured in millimeters (mm) and considered to be continuous data. The paired t-test will be used to compare the height gain after the healing following vertical ridge augmentation between the d-PTFE membrane group and the Ti-mesh group.

2. For the Aim 2, the mean incidence of post-operative complication in each group will be measured in percentage as categorical data. The Mann-Whitney U test will be used to compare the incidence of post-operative complications occurred in vertical ridge augmentation procedures between the d-PTFE membrane group and the Ti-mesh group.

3. For the Aim 3, the new bone formation will be measured in percentage as categorical data. The paired t-test will be used to compare the percentage of

new bone formation after the healing following vertical ridge augmentation between the d-PTFE membrane group and the Ti-mesh group.

All analyses will be performed using Stata (version 13.1)

Randomization:

Randomization will be performed in a 1:1 ratio using a balanced design based on a computer-generated randomization scheme, both for the location of the procedure, but also for the performed technique. Randomization will occur during visit 2.

Blinding:

The subjects will be blinded for the randomization assignment (Single-blinded). We will blind subjects by not informing them of their treatment allocation (d-PTFE membrane or Ti-mesh). If subjects do not see the preparation of the materials (d-PTFE or Ti-mesh), they will not be able to tell which procedure they receive. The preparation of d-PTFE membrane and Ti-mesh will be performed and delivered to the surgical site out of sight of participants during surgery.

C) Products

Group	Product 1	Product 2

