The pre-operative height of the bony crest will be evaluated on the pre-existing radiographs from the referring clinic if they are less than 6 months old. If recent radiographs do not exist, radiographs will be taken at this visit. Regardless of the subject's involvement in the study, it is standard of care to have radiographs taken within the past 6 months prior to surgery.

Visit 2: Surgery

Medical history will be reviewed as standard of care.

Eligibility and subject withdrawal criteria will be reviewed to ensure the subject still qualifies for the study.

Surgeries will be performed by either of two investigators.

The use of d-PTFE for vertical ridge augmentation will be randomly assigned to one side of the mouth of each subject (randomization is for research purposes) and Ti-mesh to the other side of mouth, and therefore, subjects will receive both of the following procedures:

*Guided Bone regeneration (GBR) procedure using a d-PTFE: (standard of care excluding clinical measurements)

The following steps will be performed following standard of care procedures: local anesthesia, muco-periosteal incision, full thickness flap reflection, de-cortication of the alveolar ridge, bone harvesting using bone scrapers, tenting screw placement, clinical measurements, DBBM graft material placement, the placement and stabilization of the d-PTFE membrane according to manufacturer's instructions, sutures.

* Guided Bone regeneration (GBR) procedure using Ti-mesh: (standard of care excluding clinical measurements)

The following steps will be performed following standard of care procedures: local anesthesia, muco-periosteal incision, full thickness flap reflection, de-cortication of the alveolar ridge, bone harvesting using bone scrapers, tenting screw placement, clinical measurements, DBBM graft material placement, the placement and stabilization of the titanium mesh according to manufacturer's instructions, sutures.

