If re-do of the procedure is necessary due to infection or additional need for bone grafting, the second procedure will be provided at no cost.

Subject will not be charged surgical fee of \$1,165 for one implant.

The reduction in surgical fees (both the bone augmentation surgery and implant surgery) will go into effect at the time of the visit. The subject will pay the reduced surgical fees at the time of the visit.

If the subject is in need of placement of any additional implants, he/she and/or their insurance will be responsible for the cost.

Subject will be responsible for covering the fees for the later implant crown procedures (which are not a part of this study).

If a subject withdraws or is withdrawn from the study, the reduction in fees will only apply for the time prior to the withdrawal.

(b) Transportation

No travel reimbursement and transportation costs will be provided.

(c) Payment and Insurance

If the patient has insurance policy that covers the fee of additional implants, he or she will be responsible for the co-payment only.

6) Study Results

If interested, study results will be presented to a subject upon his/her request. Study results will be given to a subject in person or via mail, according to the subject's preference, upon completion of the study. A log will be kept of the participants who are interested in receiving study results. Identifying screen failure data will be retained by the PI. Data from screen failures will be retained in the locked cabinet in the PI's office at TUSDM.

7) Confidentiality

To ensure confidentiality of subject information, each subject enrolled in the study will be assigned a unique alphanumeric code. Subjects' files will be kept in a secure, locked cabinet, within a locked room (DHS-1256) when the files are not reviewed. The information will only be shared between the researchers. All HIPAA requirements will be followed. All electronic files will be kept on a password protected computer in a secure, locked office.

a) Coding

Each subject will be assigned a subject identification number. Alphanumeric identification numbers will be assigned sequentially. This will be accessible by study personnel only. Dental records and case reports used in this study will be coded and will not include subject names.

b) Access

Only study personnel will have access to data. Investigators will permit monitoring, audits, and regulatory inspections and will provide direct access to study related documentation.

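### Does labelling bone cores by subject ID leave the Aim 3 paired comparison unable to tell d-PTFE cores from Ti-mesh cores?

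*Combined protocol and SAP*

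**What the plan says.** Section III.E, Visit 2, assigns d-PTFE at random to one side and "Ti-mesh to the other side of mouth, and therefore, subjects will receive both of the following procedures". Section III.B (Randomization) says the scheme is used "both for the location of the procedure, but also for the performed technique".

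At Visit 6 a core is taken at each implant location, and "The bone core biopsies will be placed in fixative and labeled with subject ID". The paragraph on laboratory analysis after Visit 6 adds: "The samples will be coded as subject numbers and histological analysis will be blinded". The commercial laboratory receives the cores from the PI or Co-I.

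The identifier is defined in section III.G.7 (Confidentiality, Coding): "Each subject will be assigned a subject identification number". It is a per-person number, and the same paragraph says that records will not carry names.

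Section III.B, Statistical Analysis, item 3, sets the Aim 3 test: "The paired t-test will be used to compare the percentage of" new bone between the two techniques. No section gives a side, site or sample code for the cores.

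**The concern.** In a parallel-group trial a subject number on the specimen is enough, because subject determines treatment. In a split-mouth trial it is not. Two cores from one subject, one per technique, would carry the same code, and the blinded readings would come back by subject with nothing to show which reading belongs to which barrier.

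Nothing else written in the documents makes the link:

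- The randomization list ties side to technique, not core to side.
- The tissue would not give it away, because the graft is common to both sides: "We will use a mixture of 50:50 DBBM and autogenous bone graft material for all vertical augmentation procedures in the study".
- The barrier is no longer in place when the core is taken. The listed order of steps is "membrane (Ti-mesh/d-PTFE) removal, clinical measurements, tenting screws removal, bone core harvesting".
- The plan does mention side elsewhere. The VAS surveys at Visits 3 to 5 are completed for each side, and the cores have no such wording.

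At stake would be the sign of every within-subject difference in Aim 3. An analyst cannot restore a side label that was missed at harvest.

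**Working it through.** **1. Inputs.** Seven subjects at minimum and 10 after the dropout allowance (III.B, Sample Size); two techniques per subject (III.E, Visit 2); a two-sided 5% paired t-test (III.B gives 5% and the test; two-sided is assumed). The documents give no effect or SD for new bone, so anything numerical on Aim 3 needs an assumption.

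**2. The plan's own figure.** The only calculation is for Aim 1. The difference is 5.2 − 3.15 = 2.05 mm and the pooled SD is sqrt((0.79² + 1.12²)/2) = 0.969 mm. A two-sided two-sample t-test has power 0.909 with 6 per group and 0.952 with 7. The target is 93%, so 7 is reproduced. It does not depend on core labelling.

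**3. The literal reading, worst case.** Suppose there is one core per side and side is lost for every subject. Each paired difference d_i is then known only as |d_i|.

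- Assignments that fit the report: 2^7 = 128, or 2^10 = 1,024.
- The mean difference lies between −mean|d| and +mean|d|. For normal differences with mean 0 and SD 1 (assumed), the expected mean|d| is sqrt(2/π) = 0.80 SD.
- Enumerating all assignments over simulated reports gives:

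| | 7 subjects (20,000 reports) | 10 subjects (5,000 reports) |
|---|---|---|
| Median smallest p | 0.010 | 0.002 |
| Median largest p | 0.989 | 0.999 |
| Reports that fit significance either way and also non-significance | 94.3% | 99.9% |

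The arithmetic is sound, but it describes the extremes. When the true difference is zero the differences are symmetric about zero, so on average 5% of assignments are significant: 0.05 × 128 = 6.4, or roughly 6 of 128.

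**4. Partial mix-ups.** If a share m of pairs is swapped, the expected difference shrinks by the factor (1 − 2m). Borrowing the Aim 1 difference and SDs purely as an illustration, with within-subject correlation 0 to 0.5 and 7 subjects, power in the true direction is 0.91–0.99 at m = 0, 0.54–0.61 at m = 10% and about 0.03 at m = 50%. Mislabelling would be costly if it happened.

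**5. Do the documents imply that side is lost?** Set side by side:

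- The two label sentences name the subject number. Neither says that it is the only mark on the container. Read with the Coding paragraph, their purpose is to replace names and keep the laboratory blinded. They are not a complete label specification.
- Item 3 of the Statistical Analysis compares techniques within subject. That test has meaning only if side is tracked.
- Cores are taken per implant location, so the site is known to the person holding the trephine. The mesh or membrane comes off each site in the same operation, so the technique is visible too.
- Case report forms and source documents are routinely inspected (III.G.8). These forms, and any laboratory form, are not among the documents.

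**6. A consistency test.** The Aim 1 probe readings at Visits 2 and 6 are also described with no statement that side is written down, and case reports are coded by the same subject number. If silence meant that side is not recorded, the primary outcome would be unidentified as well. Nobody would read the height measurements that way, and the cores deserve the same reading.

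**7. Do the counts fit the plan?** The figures 128 and 1,024 need exactly one core per side. Eligible spans are two or more teeth and each implant location gives a core, so a side may supply several. The study waives the surgical fee for one implant only, so some subjects may supply cores from one side only. The counts illustrate the problem; they are not a property of this trial.

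**The case for a change.** The best case for a change is that the plan sets out its core identifier twice, once beside its blinding statement, and both times stops short of what its own test needs. Cores differ from probe readings because they are physical objects that are stored, shipped and read elsewhere, and the loss would be irreversible. The remedy is a few words on a label. If side is added informally as left or right, the plan also does not say whether the laboratory can see the key.

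What stands: the text has no side code for cores, and irreversibility is a good reason for care at harvest. What does not stand is the step from an unstated label element to a comparison that cannot be carried out. Blinding is not at risk either, because left and right mean nothing to a laboratory that does not hold the randomization list. The cheapness of the remedy cuts both ways: writing down what staff would do anyway alters no estimate, test or sample size. How several cores from one side become one value is a separate question that a side code would not answer.

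**Conclusion.** The concern does not call for a change. The plan leaves a specimen-label detail unstated. The split-mouth design and the paired test leave one sensible way to fill it: mark the side or site on each core beside the subject number.

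The size is zero if side is recorded at harvest, on the label or on a form. In the worst case, the direction of the Aim 3 difference would be unknown. The documents give no basis for a probability between these two, so no expected loss can be stated.

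The conclusion assumes that trained staff running a split-mouth comparison note which side a core came from, and that the forms outside these documents allow it. A case report form with no place for side would weaken it, but the documents do not suggest that. Aim 1, the sample size of 7 and the enrolment targets are unaffected in every case.
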